12.1 CYP3A and UGT Inhibitors

Although pexidartinib does not appear to inhibit CYP drug-metabolizing enzymes to an important extent, caution is warranted when administering pexidartinib to subjects taking drugs that are highly dependent on CYP3A4 for metabolism and have a narrow therapeutic index. It is not known whether systemic exposure to these medications will demonstrate an increase while patients are receiving pexidartinib.

Of the five major CYP isoforms, 3A4 (BFC) may be involved in Phase I metabolism of pexidartinib, with possibly CYP1A2 playing a minor role (see [Attachment 5](#) for a list of common CYP3A4 inhibitors and inducers). In general, strong inducers of CYP3A4 should be avoided unless clinically necessary. These include anticonvulsants, mycin antimicrobials, and antiretrovirals. Some common examples include inducers such as rifampicin, carbamazepine, phenytoin, efavirenz, and nevirapine.

Avoid concomitant use of pexidartinib with moderate or strong CYP3A inhibitors or uridine diphosphate glucuronosyltransferase (UGT) inhibitors. If concomitant use with a moderate or strong CYP3A inhibitor or UGT inhibitor cannot be avoided, reduce the pexidartinib dose according to the recommendations in [Table 2](#). If concomitant use of a moderate or strong CYP3A inhibitor or UGT inhibitor is discontinued, increase the pexidartinib dose (after 3 plasma half-lives of the moderate or strong CYP3A inhibitor or UGT inhibitor) to the dose that was used before starting the inhibitor.

Table 2: Recommended Dosage Reductions for Pexidartinib with Concomitant Use of Moderate or Strong CYP3A Inhibitors or UGT Inhibitors

Current Total Daily Dose	Modified Total Daily Dose	Administration of Modified Total Daily Dose
800 mg	400 mg	200 mg twice daily
600 mg	400 mg	200 mg twice daily
400 mg	200 mg	200 mg once daily

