12.3 Acid-reducing Agents

Avoid the concomitant use of proton pump inhibitors (PPIs) while taking pexidartinib. As an alternative to a PPI, administer pexidartinib 2 hours before or 2 hours after taking a locally-acting antacid, or if using a histamine 2 (H₂)-receptor antagonist, administer pexidartinib at least 2 hours before or 10 hours after taking an H₂-receptor antagonist.

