ATTACHMENT 5: CYP3A4 INHIBITORS AND INDUCERS**Common CYP3A4 Inhibitors**

The following lists describe medications and foods which are common inhibitors of CYP3A4. This list should not be considered all-inclusive. Consult individual drug labels for specific information on a compound's propensity to inhibit CYP3A4.

HIV Protease Inhibitors	Others
indinavir nelfinavir ritonavir saquinavir	amiodarone cimetidine clarithromycin erythromycin fluoxetine fluvoxamine itraconazole ketoconazole mibefradil nefazodone troleandomycin verapamil
Food/Juice	
grapefruit juice	

Common CYP3A4 Inducers

The following lists describe medications which are common inducers of CYP3A4. This list should not be considered all-inclusive. Consult individual drug labels for specific information on a compound's propensity to induce CYP3A4.

HIV Antivirals	Others
efavirenz nevirapine	barbiturates carbamazepine glucocorticoids modafinil Phenobarbital phenytoin rifampin St. John's wort troglitazone rifabutin

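### Section 12.1 gives '-mycin' antimicrobials and antiretrovirals as strong CYP3A4 inducers, but Attachment 5 lists all three of its '-mycin' drugs and four of its six antiretrovirals as inhibitors

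*Combined protocol and SAP*

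**What the plan says.** Section 12.1 sets two rules for co-medication that may alter pexidartinib exposure.

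- **Inducers.** "In general, strong inducers of CYP3A4 should be avoided unless clinically necessary". The next sentence names the classes: "These include anticonvulsants, mycin antimicrobials, and antiretrovirals". Individual drugs follow: "Some common examples include inducers such as rifampicin, carbamazepine, phenytoin, efavirenz, and nevirapine". No pexidartinib dose step is stated for inducers.
- **Inhibitors.** Moderate or strong CYP3A inhibitors and UGT inhibitors are to be avoided. The text continues: "If concomitant use with a moderate or strong CYP3A inhibitor or UGT inhibitor cannot be avoided, reduce the pexidartinib dose", with the reductions given in Table 2. When the inhibitor is stopped, the dose goes back up after a stated interval.

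The paragraph that contains the inducer rule also sends the reader to Attachment 5 "for a list of common CYP3A4 inhibitors and inducers". Attachment 5 has two lists. Its inhibitor list includes the HIV protease inhibitors "indinavir nelfinavir ritonavir saquinavir" and, among the others, the run "amiodarone cimetidine clarithromycin erythromycin fluoxetine", with troleandomycin further down. Its inducer list has efavirenz and nevirapine under HIV antivirals, and rifampin and rifabutin among the others. The attachment says it is not exhaustive and refers sites to individual drug labels.

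**The concern.** The class wording in Section 12.1 carries no qualifier such as 'some'. Read as it stands, it makes any '-mycin' antimicrobial and any antiretroviral a strong inducer. Attachment 5 classifies most of the drugs that fit those descriptions the other way.

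The label matters because 12.1 attaches different instructions to the two groups: a dose reduction is linked to moderate or strong inhibitors and none to inducers. Two sites treating similar patients with the same unavoidable drug could therefore act differently, each following the protocol. The protocol reports liver enzyme abnormalities with pexidartinib, and Table 3 in Section 14.7 withholds or permanently stops treatment for them. An ambiguity about whether a dose step applies is thus more than editorial.

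**Working it through.** No sample size, power or error rate is involved, and the plan gives no figure to reproduce. The check is a count of the Attachment 5 entries by list, set against the class wording in Section 12.1.

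| Group | Section 12.1 class wording | Attachment 5: inhibitors | Attachment 5: inducers |
|---|---|---|---|
| '-mycin' drugs | strong inducers | clarithromycin, erythromycin, troleandomycin (3) | none (0) |
| Antiretrovirals | strong inducers | indinavir, nelfinavir, ritonavir, saquinavir (4) | efavirenz, nevirapine (2) |

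1. **'-mycin' drugs.** Total listed: 3 + 0 = 3. Share under inhibitors: 3/3 = 100%. The mismatch is complete.
2. **Antiretrovirals.** Total listed: 4 + 2 = 6. Share under inhibitors: 4/6 = 67%. Share under inducers: 2/6 = 33%. The mismatch is partial.
3. **Individual examples in 12.1.** Rifampicin (taken to be the same drug as rifampin), carbamazepine, phenytoin, efavirenz and nevirapine all appear in the Attachment 5 inducer list: 5 of 5 agree. None of the five ends in '-mycin', so the examples do not explain that class name.
4. **Anticonvulsants.** The two examples that 12.1 gives, carbamazepine and phenytoin, are inducers in both places. No conflict was found for this class.
5. **Where the two rules part.** If the drug can be avoided, both rules say to avoid it and the classification makes no difference. If it cannot, the inducer rule states no dose step, while the inhibitor rule leads to Table 2 provided the drug is moderate or strong.

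The fault therefore lies in two class names in one sentence of 12.1, and it has practical effect only for an unavoidable drug.

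**The case against.** The best defence is that no individually named drug is contradicted. Clarithromycin appears once in the protocol's lists, as an inhibitor, and 12.1 does not name it. The class sentence can be read as naming families in which strong inducers occur, with the examples that follow showing which ones are meant. A site that looks up the drug by name in Attachment 5 finds a single entry.

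Much of this stands. For antiretrovirals the defence works reasonably well, since both examples are inducers in both places. It fails for the '-mycin' class: Attachment 5 has no '-mycin' inducer, and 12.1 offers no '-mycin' example. Perhaps rifampicin and rifabutin were meant, but the text leaves the reader to guess.

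A reader might also infer more than the documents support:

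- **That sites are told to apply opposite rules.** Both rules start with avoidance. For inducers, 12.1 is silent on dose; it does not say that the dose stays unchanged.
- **That Table 2 applies to clarithromycin or the protease inhibitors.** Table 2 depends on a moderate or strong grade. Attachment 5 grades no drug, so the documents do not show which entries qualify.
- **That a misclassified patient takes 1.5 to 2 times the intended dose.** These are the Table 2 ratios (600/400 = 1.5; 800/400 and 400/200 = 2). Besides needing the missing grade, they do not cover the assigned extension dose of 1000 mg/day, for which Table 2 has no row.
- **That Section 12.3 conflicts with Attachment 5 over cimetidine.** Section 12.3 gives timing advice for acid reduction ("administer pexidartinib at least 2 hours before or 10 hours after taking an" an H2-receptor antagonist). It exempts no drug from 12.1, and both sections can apply together.
- **That the pharmacokinetic review in Section 24.3 would get the direction of effect wrong.** Section 24.3 does not plan to code drugs by the 12.1 classes, and Section 12.0 has generic names recorded, so each drug can be classified individually.

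**Conclusion.** The contradiction is real, and the sentence in 12.1 is wrong as written. In Attachment 5 it disagrees with 3 of 3 '-mycin' drugs and 4 of 6 antiretrovirals. It bears on an operative safety instruction, because a dose step is tied to one classification and not to the other. Its reach is limited to drugs that cannot be avoided and to sites that follow the class name over the drug list.

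The conclusion rests on reading the class sentence literally, on treating rifampicin and rifampin as the same drug, and on counts from a list that says it is incomplete. 'Four of six' therefore describes the listed antiretrovirals, not the whole class. The documents do not say how many patients are affected. No endpoint or planned analysis is shown to depend on the sentence, and the documents do not support a statement about the size of any effect on exposure.

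**What to change.** Reconcile Section 12.1 with Attachment 5. In 12.1, replace the two class names (the '-mycin' antimicrobials and the antiretrovirals) with individual drugs. Put each drug under one heading only, inhibitor or inducer, and make the two places identical. The sponsor decides each classification; no dose or clinical rule is proposed here.

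The cost is a wording change to one sentence of 12.1 and, if needed, matching entries in Attachment 5. It needs no new procedure, assessment or data.

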	
 a. For advanced or recurrent MEC of the salivary gland, patients must not be candidates for curative surgery or radiotherapy. b. For PVNS (including tenosynovial giant cell tumor), patients must have a histologically confirmed diagnosis of inoperable progressive or relapsing PVNS, or resectable tumor requiring mutilating surgery, as well as demonstrated progressive disease in the last 12 months. c. For GIST, patients must have failed previous therapy with imatinib and sunitinib. Patients with known PDGFR mutations are excluded, but mutation testing is not required for study entry. d. For ATC, patients must have histologically or cytologically diagnosed advanced ATC. e. For metastatic solid tumors with documented malignant pleural, pericardial, and/or peritoneal effusions, patients must not be receiving specific therapy for the effusion (other than periodic drainage by needle) or have an indwelling drain. f. Other solid tumor types can be included in a miscellaneous cohort, provided there is a clear scientific rationale for treatment with pexidartinib and upon approval by the Medical Monitor. 
 4. Women of child-bearing potential must have a negative pregnancy test within 7 days of initiation of dosing and must agree to use an acceptable non-hormonal method of birth control from the time of the negative pregnancy test for one month after the last dose of study drug. Highly effective non-hormonal methods of contraception include: intra-uterine device (non-hormonal), bilateral tubal occlusion, vasectomy, sexual abstinence, or barrier methods (e.g., condom, diaphragm). Women of non-childbearing potential may be included if they are either surgically sterile or have been postmenopausal for ≥ 1 year. Fertile men must also agree to use an acceptable method of birth control while on study drug and for one month after the last dose of study drug. 5. All associated toxicity from previous or concurrent cancer therapy must be resolved (to \leq Grade 1 or Baseline) prior to administration of pexidartinib. 6. Willing and able to provide written informed consent prior to any study related procedures and to comply with all study requirements. 7. ECOG performance status 0 or 1. 8. Life expectancy ≥ 3 months. 9. Adequate hematologic, hepatic, and renal function (absolute neutrophil count $\geq 1.5 \times 10^9/L$, Hgb > 9 g/dL, platelet count $\geq 100 \times 10^9/L$, AST/ALT $\leq 2.5 \times$ ULN or $< 5 \times$ ULN in the presence of liver metastases, albumin ≥ 3 g/dL, creatinine $\leq 1.5 \times$ ULN or calculated CrCl > 60 mL/min using Cockcroft-Gault formula). 
Exclusion
 
 1. Specific anti-cancer therapy within 3 weeks prior to study drug administration. 2. Investigational drug use within 28 days of the first dose of pexidartinib. 3. Uncontrolled intercurrent illness. 4. Refractory nausea and vomiting, malabsorption, external biliary shunt, or significant small bowel resection that would preclude adequate absorption. 5. QTcF ≥ 450 msec (for males) or ≥ 470 msec (for females) at screening. 6. The presence of a medical or psychiatric condition that, in the opinion of the Principal Investigator, makes the patient inappropriate for inclusion in this study.

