Dosage and Regimen	
The proposed starting dose is 200 mg QD. A BID dosing regimen may be used in subsequent cohorts, pending review of the PK from the initial cohort.
 
Cohorts of patients with solid tumors will be enrolled using 100% dose increments in the absence of drug-attributable Grade 2 toxicity. In each cohort (and following the one-week run-in period for applicable patients), the first patient will be observed for at least one week before additional patients in that cohort are treated with pexidartinib. Following the one-week run-in period for applicable patients, upon the occurrence of Grade 2 or greater drug-attributable toxicity, in the absence of dose limiting toxicity (DLT), dose escalation will proceed sequentially by 50% increments. From that point forward, the standard "3+3" design will be used. Following the one-week run-in period for applicable patients, if DLT is observed in one patient at a given cohort, at least 6 patients will be treated at that dose. Following the one-week run-in period for applicable patients, if DLT is observed in 2 or more of 6 patients at a dose level, then the next lower dose level will be expanded or an intermediate dose level will be introduced. The MTD is defined as the dose at which ≤ 1 of 6 patients experience a DLT during Cycle 1, with the next higher dose having at least 2 of the up to 6 patients experiencing a DLT during Cycle 1. If no DLT is observed, the recommended dose for further evaluation will be established based on toxicity, PK, and convenience of dosing in approximately 3–6 patients treated at that dose. Dose escalation will only be permitted if adequate safety and tolerability have been demonstrated at the previous lower dose for 28 days.
 
The dosage for the Extension cohorts will be the RP2D level of 1000 mg/day, using a BID regimen.

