After the initial 4 weeks of dosing, all patients will be able to continue receiving pexidartinib at their assigned dose provided they meet the criteria described in [Section 13.8](#). Patients will return for clinical evaluation every 28 days and will have radiographic assessments (solid tumors) for response and progression after every two months of drug administration.

Extension Cohorts:

At the recommended Phase 2 dose of 1000 mg/day, a total of six Extension cohorts will be enrolled and followed for safety and tumor response as assessed by CT scan every 8 weeks (or, beyond Cycle 40, every 24 weeks). Participants will remain on treatment until tumor progression, as long as there are no unacceptable toxicities.

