5. All associated toxicity from previous or concurrent cancer therapy must be resolved (to \leq Grade 1 or Baseline) prior to administration of pexidartinib.

6. Willing and able to provide written informed consent prior to any study related procedures and to comply with all study requirements.
7. ECOG performance status 0 or 1.
8. Life expectancy ≥ 3 months.
9. Adequate hematologic, hepatic, and renal function (absolute neutrophil count $\geq 1.5 \times 10^9/L$, Hgb >9 g/dL, platelet count $\geq 100 \times 10^9/L$, AST/ALT $\leq 2.5 \times$ ULN or $<5 \times$ ULN in the presence of liver metastases, albumin ≥ 3 g/dL, creatinine $\leq 1.5 \times$ ULN or calculated CrCl >60 mL/min using Cockcroft-Gault formula).

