14.7 Dose Modification (Extension Cohorts)

Reduction/interruption of dosing for adverse events may take place at any time during the study according to guidelines in [Table 3](#). Dose reductions should occur in increments of 200 mg/day, depending on the toxicity grade, as noted in [Table 3](#). Dose reduction/interruption guidelines for hematologic and nonhematologic treatment-related TEAEs are based on severity. Dose interruptions can be implemented at the discretion of the treating Investigator to manage intolerable or clinically significant toxicity. If a dose interruption is required, study assessments should be performed as scheduled, irrespective of the study drug delay, with the exception of PK assessments, which should be deferred until treatment is resumed. Interruptions due to toxicity

lasting >3 weeks require treatment discontinuation unless the medical monitor approves continuation.

Table 3: Dose Modifications

Event	Severity	Pexidartinib Dosage Modifications
Hepatotoxicity		
Increased ALT and/or AST	>3 to 5 × ULN	Withhold and monitor liver tests weekly. If AST and ALT ≤3 × ULN within 4 weeks, resume at reduced dose. If AST or ALT not ≤3 × ULN in 4 weeks, permanently discontinue pexidartinib.
	>5 to 10 × ULN	Withhold and monitor liver tests twice weekly. If AST and ALT ≤3 × ULN within 4 weeks, resume at reduced dose. If AST or ALT not ≤3 × ULN in 4 weeks, permanently discontinue pexidartinib.
	>10 × ULN	Permanently discontinue pexidartinib. Monitor liver tests twice weekly until AST or ALT ≤5 × ULN, then weekly until ≤3 × ULN.
Increased ALP ^a and GGT	ALP >2 × ULN with reflex test of GGT >2 × ULN	Permanently discontinue pexidartinib. Monitor liver tests including GGT twice weekly until ALP ≤5 times ULN, then weekly until ≤2 × ULN.
Increased bilirubin	TB >ULN to <2 × ULN or DB >ULN and <1.5 × ULN	Withhold and monitor liver tests twice weekly. If an alternate cause for increased bilirubin is confirmed and bilirubin <ULN within 4 weeks, resume at reduced dose. If bilirubin not <ULN in 4 weeks, permanently discontinue pexidartinib.
	TB ≥2 × ULN or DB >1.5 × ULN	Permanently discontinue pexidartinib. Monitor liver tests twice weekly until bilirubin ≤ULN.
Adverse Reactions or Other Laboratory Abnormalities		
Any	Severe or intolerable	Withhold until improvement or resolution. Resume at a reduced dose upon improvement or resolution.

ALT = alanine aminotransferase; ALP = alkaline phosphatase; AST = aspartate aminotransferase;

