14.7.1 Renal Impairment

A reduced dose of 600 mg/day (200 mg in the morning and 400 mg in the evening) is recommended in study subjects with mild to severe renal impairment (creatinine clearance [CL_{cr}] 15 to 89 mL/min estimated by Cockcroft-Gault using actual body weight).

14.8 End of Study/Early Withdrawal (last dose for subjects that enroll in phase 4 continuation study or immediately transition to commercial pexidartinib; last + 30 ± 7 days for all other subjects)

Note: In order to be eligible to participate in the phase 4 PVNS continuation study, subjects must not be withdrawn from PLX108-01 until they are ready to begin screening in the phase 4 continuation study. Screening for the phase 4 continuation study may occur prior to withdrawal from PLX108-01.

Following the last dose of drug, all patients will have the following evaluations:

1. Physical examination including weight (kg) and vital signs (sitting blood pressure, pulse rate, and respiratory rate, and oral temperature [°F]).
2. Standard 12-lead ECG to determine QTcF.
3. Clinical laboratory evaluation (hematology, chemistry, urinalysis, serum pregnancy test (women of child-bearing potential).
4. ECOG Performance status assessment.
5. For patients enrolled after the implementation of Amendment 8, collect the six (6) completed NRS for PVNS Symptoms questionnaires and give the patient another one of the questionnaires to complete predose. NOTE: the NRS for PVNS Symptoms questionnaire to be completed in the clinic is exactly the same as the other 6 daily questionnaires.
6. For patients enrolled after the implementation of Amendment 8, then give the patient the Western Ontario and McMaster Universities Osteoarthritis Index (WOMAC) questionnaire to complete predose. NOTE: At each of the applicable visits, sites should refrain from providing any interpretation of how the questions should be answered by the patient.
7. Radiographic assessment of tumor burden.
8. Test article compliance.
9. Concomitant medications.
10. Collection of surgical data - If surgical resection of the tumor is performed within 30 days of the last dose of study treatment, details of the surgery and its outcome should be obtained.

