16.0 TEST ARTICLE

16.1 Test Article Administration

Test article (study drug) will be administered only to patients who have signed and dated an informed consent form. Test article will be administered on days 1 through 28 or longer in the fasting state with 240 mL (8 oz.) of room-temperature water. The patient should fast at least 2 hours before administration and 1 hour after administration of the test article. Patients will be permitted to eat a low-fat snack (e.g., crackers, toast, tea) during the fasting period if needed. Test article will be taken orally by swallowing the capsules. For patients with tumors of the head and neck area who may have difficulty swallowing capsules, test article may be administered by emptying the contents of the dose (e.g., 3 x 200 mg capsules in the morning, and 2 x 200 mg capsules in the evening for a total daily dose of 1000 mg/day) into an empty glass.

Approximately 6 ounces of orange juice, apple juice, or cola should be added to the glass, stirred vigorously with a spoon and the patient should drink the contents, add 2 additional ounces to the glass, stir again and drink the remaining contents. The entire dose should be consumed within 30 minutes and the capsule shells should be discarded in a bio-disposable hazard bag provided by the site. NOTE: The Plexxikon Medical Monitor must be consulted prior to implementation of this alternative method of test article administration.

Test article administration will start on C1D1 and should be taken once daily for the initial cohort. Subsequent cohorts may utilize a twice daily dosing regimen, with study drug being administered at approximately 12-hour intervals. On PK collection C1D1 and C1D15, the patients will be administered pexidartinib capsules at the clinical site. The time of the administration will be recorded. On non-PK collection days, patients will administer the study drug at home. Missed doses (i.e., outside of a + 2-hour window) should be skipped and not administered as a double dose at the next administration. Patients who vomit their dose should be instructed to NOT to make up that dose. Patients should take precautions to prevent accidental ingestion of or exposure to investigational drug by family members or other cohabitants.

Food-Effect Assessment:

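### Table 2, the dose-reduction table for unavoidable CYP3A or UGT inhibitors, has no row for the 1000 mg/day assigned to the Extension cohorts

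*Combined protocol and SAP*

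**What the plan says.** **Assigned dose.** The Synopsis (Dosage and Regimen) states: "The dosage for the Extension cohorts will be the RP2D level of 1000 mg/day, using a BID regimen". Section 9.1 agrees: "At the recommended Phase 2 dose of 1000 mg/day, a total of six Extension cohorts will be enrolled". Section 16.1, describing administration for patients who have difficulty swallowing capsules, gives as its example three 200 mg capsules in the morning and "2 x 200 mg capsules in the evening for a total daily dose of 1000 mg/day". Sections 14.6.1 and 14.6.2 continue treatment at the assigned dose, both up to and after Cycle 40.

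**Inhibitors.** Section 12.1 first says to avoid moderate or strong CYP3A inhibitors and UGT inhibitors. As a fallback, if such a drug "cannot be avoided, reduce the pexidartinib dose according to the recommendations in" Table 2. The table has three rows by current total daily dose: 800 mg goes to 400 mg, 600 mg to 400 mg, and 400 mg to 200 mg. When the inhibitor is stopped, the patient returns to the previous dose after a stated interval.

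**Other reductions.** Section 14.7 covers adverse events in the Extension cohorts: "Dose reductions should occur in increments of 200 mg/day, depending on the toxicity grade". Section 14.7.1 covers renal function: "A reduced dose of 600 mg/day (200 mg in the morning and 400 mg in the evening) is recommended in study subjects" with creatinine clearance of 15 to 89 mL/min.

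**The concern.** The fallback in Section 12.1 limits exposure when an interacting drug has to be given. It works only if the patient's current dose appears in Table 2. The dose assigned to the Extension cohorts, from which every reduction under Section 14.7 starts, does not appear.

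Followed literally, the text reduces a patient on 800, 600 or 400 mg/day but states no reduction for a patient on 1000 mg/day, the highest dose in these cohorts. Section 14.7 itself notes that liver enzyme abnormalities have occurred with the drug, and Attachment 5 lists common CYP3A4 inhibitors, so the situation is foreseeable. Section 9.3 allows up to approximately 18 Extension sites. Without a stated answer, each would have to settle the matter for itself, and they could settle it differently.

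**Working it through.** No power, alpha or sample-size figure is involved. The check is whether the assigned dose is covered by the table, by a rule implied by the table, or by another section.

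**1. Confirm the assigned dose.** From Section 16.1: 3 × 200 mg + 2 × 200 mg = 600 + 400 = 1000 mg/day. This agrees with the Synopsis and Section 9.1.

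**2. Look it up in Table 2.** Below are 1000 mg/day and the doses reached from it in the 200 mg/day steps of Section 14.7.

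| Current dose (mg/day) | Row in Table 2? |
|---|---|
| 1000 | No |
| 800 | Yes |
| 600 | Yes |
| 400 | Yes |
| 200 | No |

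The table has a header and three complete rows, with no sign of redaction or text lost in conversion.

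**3. Test whether the rows imply a rule.** Fraction retained = modified dose / current dose. Cut = current dose − modified dose.

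| Current (mg) | Modified (mg) | Fraction retained | Cut (mg) |
|---|---|---|---|
| 800 | 400 | 400/800 = 50% | 800 − 400 = 400 |
| 600 | 400 | 400/600 = 67% | 600 − 400 = 200 |
| 400 | 200 | 200/400 = 50% | 400 − 200 = 200 |

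Neither column is constant, so no single ratio or step reproduces all three rows. The table therefore does not fix an entry for 1000 mg/day.

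**4. Look for the rule elsewhere.**
- Section 14.7: its 200 mg/day steps depend on toxicity grade. They respond to an event that has occurred, not to a co-medication.
- Table 3: covers hepatotoxicity and other adverse reactions or laboratory abnormalities. Table 4 covers liver work-up. Neither mentions interacting drugs.
- Section 12.1: does not refer an unlisted dose to the Medical Monitor or to any other source. Its rule for returning to the previous dose works from any dose, but its rule for reducing does not.
- Section 14.7.1: concerns creatinine clearance only.

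None of these supplies an answer at 1000 mg/day.

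**5. Renal text, for completeness.** 200 + 400 = 600 mg/day, so Section 14.7.1 is arithmetically consistent, and 600 mg/day has a row in Table 2. Inclusion item 9 admits patients with "calculated CrCl >60 mL/min using Cockcroft-Gault formula" or, as an alternative, creatinine up to 1.5 × ULN. The clearance criterion (>60 mL/min) and the renal range (15 to 89 mL/min) overlap at >60 to 89 mL/min.

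**The case against.** The strongest reply is that the gap is narrow. The primary instruction in Section 12.1 is avoidance, and that can be followed at any dose. Table 2 serves only the fallback, and its entries are called recommendations. A patient already reduced for toxicity to 800, 600 or 400 mg/day has a row. The current text describes a study in long-term follow-up, with visits after Cycle 40 and transition to a phase 4 study or commercial drug, so few patients may still be on 1000 mg/day. No endpoint, analysis set or decision rule is affected.

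All of this stands as a limit on scope. A reader might infer from the missing row that the Extension cohorts in general have no guidance on inhibitors; the documents do not support that. But none of it closes the gap: Section 12.1 provides for the case where avoidance fails, and the table it relies on omits the assigned dose.

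Three other stronger readings should be set aside.

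- A reader might extend the table's patterns to 1000 mg/day and report a range of candidate doses as the size of the problem. Such figures would be the reader's own construction. The unequal ratios and steps already show that no answer is determined.
- A reader might infer that Section 14.7.1 contradicts the assigned dose, because some eligible patients fall under both. It does not. It gives an absolute target for a defined clearance range and can be applied as an exception to 1000 mg/day. At most a cross-reference is missing.
- A reader might count other unlisted doses, such as the 200 mg starting dose of the escalation phase. The conclusion does not rest on these.

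**Conclusion.** The point holds as an internal inconsistency and should be fixed. The instruction in Section 12.1 gives no answer for an Extension patient on the assigned 1000 mg/day, and neither Table 2 nor any other section supplies one.

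Its size is one absent row at one dose, which is the dose the Synopsis and Section 9.1 assign to all six Extension cohorts. It matters only for patients still on 1000 mg/day whose inhibitor cannot be avoided; the documents do not say how many there are. That the omission exists is certain from the text. That sites would handle it differently is inference.

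The conclusion assumes that Table 2 is complete as printed and that 1000 mg/day remains the assigned dose, as the Synopsis, Section 9.1 and Section 16.1 all state. The renal overlap is a minor editorial note and adds no weight.

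**What to change.** The sponsor should reconcile Section 12.1 and Table 2 with the 1000 mg/day in the Synopsis, Section 9.1 and Section 16.1, so that the table or its accompanying text says what applies at the assigned dose. The dose value and the clinical rule are for the sponsor to decide; none is suggested here.

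Optionally, in the same revision, cross-refer to Section 14.7.1 where the Synopsis and Section 9.1 assign 1000 mg/day, since its clearance range overlaps with inclusion item 9.

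The cost is one table entry or one sentence, plus the optional cross-references, handled through the amendment process in Section 29.0 if the sponsor regards the change as significant. No data collection, analysis or sample-size figure changes.
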